### **Analytical Plan**

Results will be analyzed initially using descriptive statistics. Comparison between groups will be done using chi square tests for proportions, and t-tests or ANOVA procedures for continuous variables. Regression analysis will be performed to identify independent outcome predictors. Other inferential statistical analysis will be conducted as appropriate.

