## **MATERIALS AND METHODS**

### **Design**

This is a single center, prospective, randomized clinical trial. Subjects will consist of patients referred to the urology clinic at Wake Forest University Baptist Medical Center with interstitial cystitis for whom conservative management/oral medications have failed and Onabotulinumtoxin A is recommended. These patients will all have undergone evaluation by [name]: an expert in the management of pelvic pain syndromes who sees >300 new patients each year.

Upon initial evaluation all subjects will undergo assessment including history taking and physical examination, urinalysis, subjective symptom assessment using self-reporting questionnaires, and objective symptom assessment using uroflowometry as well as the measurement of post void residuals.

After initial assessment subjects will be randomized into either the control or experimental cohorts. Subjects will receive a single dose of PO ciprofloxacin prior to injection unless culture or allergies dictate to use a different antibiotic. Each group will receive a total of 100 units of botox spread out among 10 separate injections. Subjects in the control group will have 10 injections made about the periphery of the trigone.

Subjects in the experimental cohort will receive a one time dose of 100 units of Onabotulinumtoxin A diluted in 10 mL of preservative free normal saline and injected in 1.0 mL boluses in a set pattern across the upper aspect of the trigone of the urinary bladder. Meanwhile, those subjects randomized to the control cohort will also receive a one time dose of Onabotulinumtoxin A using the same dilution and number of boluses, but boluses will be administered at random sites on the posterior bladder wall (excluding the trigone). Post –treatment, subjects will remain at the site for at least 30 minutes for observation and will demonstrate their ability to void before leaving. All procedures will be performed using the facilities of Wake Forest Baptist Medical Center.

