### **Subject selection criteria**

Written informed consent will be obtained from all subjects before enrollment. Once participants have been appropriately consented, the minimal amount of clinical data required will be abstracted from their electronic medical record. Other extracted information will include their past medical history, such as comorbidities, current medications, and any symptoms of IC they experience. Furthermore, physical exam findings, laboratory results, intra-operative findings, and pathology reports will be reviewed. Patients will complete questionnaires that have been well-established to assist in IC diagnosis and assessment of disease severity and response to treatment, and are part of routine clinical diagnosis and treatment. These include the O'Leary-Sant Interstitial and the Pelvic Pain and Urgency/Frequency Patient Symptom Scale (PUF). Each of these questionnaires are well established in the literature to help the urologist identify and treat patients with IC. Their scores on these questionnaires must >10 for either the ICSS or ICPI, and >10 on the PUF. Both the O'Leary/Sant questionnaire and PUF questionnaire ask about the voiding patterns and pain levels of IC patients.

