### **Power Analysis**

We expect that treatment will result in a large effect and as such have set an anticipated Cohen's  $d$  as 0.95. Using this value along with standard study values of  $\alpha=0.05$  and  $\beta=0.80$  we calculated a minimum total study group requirement of 38 subjects with 19 subjects in each arm.

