### **Outcome Measure(s)**

The primary outcome will be a measurement of subjective patient pain using the Pelvic Pain and Urinary Urgency Frequency (PUF) questionnaire and the O'Leary-Sant Symptom and Problem Indexes. Patients will be asked to complete this questionnaire prior to treatment administration and at 30 and 90 days post treatment. The PUF and O'Leary Sant are previously validated tools that have been used by numerous researchers to evaluate pelvic pain. Secondary outcomes will be objective data as to patient performance in uroflowmetry as well as measurement of post void residuals. Patients will

again undergo these assessments prior to treatment and at 30 and 90 days post treatment to assess objective treatment effectiveness.

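### The arm comparison of continuous outcomes has no baseline adjustment and no choice between follow-up and change scores; a pre-specified ANCOVA costs about one power point at worst and gains power once the baseline correlation exceeds about 0.17

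*Combined protocol and SAP*

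**What the plan says.** The Analytical Plan is one short paragraph. For the arm comparison it states: "Comparison between groups will be done using chi square tests for proportions, and t-tests or ANOVA procedures for continuous variables". Two further sentences could bear on the point. One is "Regression analysis will be performed to identify independent outcome predictors", which names no covariates and is not tied to the comparison of arms. The other is "Other inferential statistical analysis will be conducted as appropriate", which commits to nothing.

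Baseline values exist for every outcome. Outcome Measure(s) says of the questionnaires: "Patients will be asked to complete this questionnaire prior to treatment administration and at 30 and 90 days post treatment". It says of uroflowmetry and post-void residual that patients will "again undergo these assessments prior to treatment and at 30 and 90 days post treatment to assess objective treatment effectiveness". The visit schedule under Design agrees.

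Power Analysis sets Cohen's d at 0.95 and arrives at a "minimum total study group requirement of 38 subjects with 19 subjects in each arm". It does not say whether d refers to the SD of follow-up scores or of change scores. Sample Size and Randomization then plans 20 per arm. No section mentions analysis of covariance, a baseline covariate or a change-score analysis.

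**The concern.** The wording allows at least two different tests of the same question: a t-test on the follow-up score and a t-test on the change from baseline. Their power differs, and which is better depends on the correlation r between baseline and follow-up and on the SD behind d. The plan gives neither. ANCOVA on the follow-up score, with baseline as covariate, uses the same data and stays near or above the better of the two.

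Two things are at stake. The first is power in a trial of 40 patients that sits one patient per arm above its own minimum. The second is the false-positive rate: if the response variable is chosen after results are seen, the nominal 5% no longer holds. Chance baseline imbalance is a smaller matter, because the t-test's standard error already allows for it.

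**Working it through.** **Inputs.** From the documents: d = 0.95, alpha 0.05, 19 per arm as minimum (Power Analysis); 20 per arm planned (Sample Size and Randomization). The stated beta of 0.80 is read as power of 0.80, and the test is taken as two-sided because that reproduces the stated size. Assumed: r = 0, 0.3, 0.5 or 0.7; normal scores; equal SD (set to 1) at baseline and follow-up; a linear relation.

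**The plan's own figure.** For an unadjusted two-sided t-test, noncentral t gives 79.1% power at 18 per arm, 81.3% at 19 and 83.3% at 20. The stated 19 per arm reproduces.

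**Variance of the arm difference, relative to a follow-up t-test** (N = total sample size):

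- follow-up score: 1
- change score: 2(1 − r)
- ANCOVA: (1 − r²)(N − 3)/(N − 4), where the last factor is the cost of estimating the slope

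**Break-even.** ANCOVA equals the follow-up t-test in variance at r = √(1/(N − 3)). At N = 38 this is √(1/35) = 0.169; at N = 40 it is √(1/37) = 0.164. On power at N = 40 the crossing is at 0.168. Against the change score, ANCOVA has the lower variance while (1 + r)(37/36) < 2, that is, for r below 72/37 − 1 = 0.95 at N = 40.

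**Power at 20 per arm.** Because the SD behind d is not stated, both readings are shown. Scale A puts d on the follow-up SD, so the effect is 0.95. Scale B puts d on the change-score SD, so the effect is 0.95 × √(2(1 − r)) = 1.34, 1.12, 0.95 and 0.74 follow-up SDs. The t-tests use noncentral t with 38 df; ANCOVA uses noncentral t with 37 df, averaged over the chance baseline imbalance.

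| Scale | Test | r = 0 | r = 0.3 | r = 0.5 | r = 0.7 |
|---|---|---|---|---|---|
| A | Follow-up t-test | 83.3% | 83.3% | 83.3% | 83.3% |
| A | Change-score t-test | 54.4% | 69.7% | 83.3% | 96.6% |
| A | ANCOVA | 82.3% | 85.7% | 91.5% | 98.1% |
| B | Follow-up t-test | 98.5% | 93.4% | 83.3% | 62.1% |
| B | Change-score t-test | 83.3% | 83.3% | 83.3% | 83.3% |
| B | ANCOVA | 98.3% | 94.7% | 91.5% | 87.9% |

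The lowest value over both scales is 62% for the follow-up t-test, 54% for the change-score t-test and 82% for ANCOVA.

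**False positives from an open choice.** Under no arm difference, simulation of the chance that at least one of the two t-tests is significant gives about 8.5% at r = 0, rising to about 9.4% at r = 0.7. This is for one score at one visit.

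**Baseline imbalance.** One standard error of the baseline difference is √(2/20) = 0.316 SD. Only r times this carries into the follow-up difference: 0.09 SD at r = 0.3 and 0.16 SD at r = 0.5.

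**Effect of the entry rule.** Subject selection criteria requires: "Their scores on these questionnaires must >10 for either the ICSS or ICPI, and >10 on the PUF". A cut-off narrows the baseline range and may lower r. With v the variance of a standard normal truncated from below, the correlation becomes r√v / √(r²v + 1 − r²). The cut positions below are assumptions, because the documents give no score distribution.

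| Assumed cut | v | r = 0.3 becomes | r = 0.5 becomes | r = 0.7 becomes |
|---|---|---|---|---|
| 1 SD below the mean | 0.630 | 0.24 | 0.42 | 0.61 |
| At the mean | 0.363 | 0.19 | 0.33 | 0.51 |

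With the cut at the mean and d on the observed follow-up SD, simulated power is about 83/86/92% for ANCOVA, 83% for the follow-up t-test and 78/83/91% for the change-score t-test, at pre-cut r of 0.3/0.5/0.7.

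**The case against.** The strongest reply is that nothing is broken. The t-test is valid under randomization, and where the tested score matches the scale of d, power is 83% at every r. The 54% and 62% cells arise only if the trial was powered on one scale and tested on the other, at the ends of the range of r. That is correct, and these cells should not be read as the plan's expected power. They show what the wording permits while the scale of d and the response variable are both unstated.

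Second, the gain depends on an unknown r and shrinks under the entry rule. This also stands. With the cut at the mean, the gain over the follow-up t-test is about 0, 3 and 8 points at pre-cut r of 0.3, 0.5 and 0.7, and a pre-cut r of 0.2 would fall below break-even (0.16 or 0.12 under the two cuts). Even there the loss is at most about 1 point.

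Third, the reference to ANOVA could cover a repeated-measures analysis, and the planned regression could include arm and baseline. But a group-by-time ANOVA on baseline and one follow-up visit is equivalent to the change-score t-test, and the regression is described only as a search for predictors. Neither fixes the comparison.

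Fourth, the larger freedom lies in three scores at two visits, which ANCOVA does not resolve. That is true and needs its own sentence. Also, the calculations assume normal scores, so the size of any gain for uroflowmetry and post-void residual is untested.

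**Conclusion.** The concern holds, as a recommended improvement and not as an error. The plan leaves the response variable and the use of baseline open for every continuous outcome, and a better method is available from data already being collected.

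On the follow-up SD scale at 20 per arm, ANCOVA changes power relative to the follow-up t-test by about −1, +2, +8 and +15 points at r = 0, 0.3, 0.5 and 0.7. Against the change-score t-test it gains about 28, 16, 8 and 2 points. The gain over the follow-up t-test may be close to zero if the entry cut-offs restrict the baseline range strongly. Fixing the response in advance also removes the rise from 5% to roughly 8.5–9.4% false positives that after-the-fact selection between the two t-tests would allow.

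These figures rest on assumed correlations, equal SDs, normality and linearity. The break-even near 0.17 needs no value of r from the documents; it follows from the sample size and, on the power scale, the stated d.

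**What to change.** In the Analytical Plan, replace the wording for continuous outcomes with:

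> Each continuous outcome at a follow-up visit will be compared between arms by analysis of covariance, with arm as factor and the baseline value of the same measure as covariate. The adjusted mean difference and its 95% confidence interval will be reported.

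Keep N at 40. The change should be made before outcome data are seen. It needs no extra data and spends one degree of freedom, which costs about 1 point of power if r is near zero.

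The sentence settles follow-up versus change and adjusts only for the measured baseline value. It does not settle which of the three scores (PUF, symptom index, problem index) and which of the two visits is primary; a separate sentence should do that. Power Analysis should also state which SD the d of 0.95 refers to.

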### **Sample Size and Randomization**

Each study arm will consist of 20 subjects for a total study population of 40. This number was chosen using estimates of symptom relief using our current patient population as reference.

Patients will be randomized to either the control or experimental cohort using a computer generated randomization table. Providers will not be aware of the subjects' cohort status until immediately prior to injection.

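### The Analytical Plan does not say how missing day 90 scores are handled; a baseline-adjusted repeated-measures model would protect the site comparison better than an unspecified t-test or ANOVA

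*Combined protocol and SAP*

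**What the plan says.** - **Outcome.** Under Outcome Measure(s): "The primary outcome will be a measurement of subjective patient pain using the Pelvic Pain and Urinary Urgency Frequency (PUF) questionnaire", together with the O'Leary-Sant indexes. Scores are taken "prior to treatment administration and at 30 and 90 days post treatment". Neither one scale nor one visit is named as primary.
- **Analysis.** The Analytical Plan compares arms by "t-tests or ANOVA procedures for continuous variables", adds regression to look for predictors, and ends: "Other inferential statistical analysis will be conducted as appropriate".
- **Sample size.** The Power Analysis uses Cohen's d of 0.95 and arrives at a "minimum total study group requirement of 38 subjects with 19 subjects in each arm". Sample Size and Randomization says: "Each study arm will consist of 20 subjects for a total study population of 40". The basis offered there is symptom relief: "This number was chosen using estimates of symptom relief using our current patient population as reference". It does not mention attrition.
- **Visits.** In the schedule under Design, the day 45 and day 60 phone calls collect only adverse events and medications. No questionnaire falls between day 30 and day 90 that could stand in for a missed day 90 score.
- **Not stated anywhere.** There is no analysis set, intention-to-treat statement, missing-data method, expected dropout rate or dropout allowance.

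**The concern.** On any ordinary reading, the named methods lose the patients who miss day 90. A t-test on the day 90 score, a t-test on change from baseline and a one-way ANOVA all need the day 90 value. A classical repeated-measures ANOVA deletes incomplete cases, so it also discards those patients' day 30 scores.

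This matters if missingness is related to outcome. Patients are refractory at entry, and the trial's hypothesis is that the posterior-wall arm improves less. If poor responders stay away more often, more of them leave that arm and the completer means move together. The trial could then understate a real site difference, or miss it, although the day 30 scores that signal the loss are in the database. With one patient per arm above the minimum, even random loss soon takes power below 80%.

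**Working it through.** **1. Reproduce the plan's figure.** Inputs from the Power Analysis are d = 0.95, α = 0.05 and 80% power. The section prints 0.80 as β; I read it as power. Sidedness is not stated, but a two-sided test reproduces the stated number. For n per arm, the noncentrality is δ = d × √(n/2), and power is the probability that a noncentral t on 2n − 2 degrees of freedom exceeds its two-sided 5% critical value.

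For n = 19: δ = 0.95 × √9.5 = 2.93, power 81.3%. For n = 18: δ = 0.95 × √9 = 2.85, power 79.1%. So 19 per arm, 38 in total, is correct for complete data.

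**2. Random loss only.** Same formula, starting from 20 per arm:

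| Day 90 scores per arm | Loss | Power |
|---|---|---|
| 20 | 0% | 83.3% |
| 19 | 5% | 81.3% |
| 18 | 10% | 79.1% |
| 17 | 15% | 76.6% |
| 16 | 20% | 73.9% |

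Keeping 19 day 90 scores per arm would need 19/0.90 = 21.1, so 22 per arm, at 10% loss, and 19/0.80 = 23.75, so 24 per arm, at 20%.

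**3. Loss related to outcome.** This was simulated with 20 per arm, unit SD and a true difference of 0.95 SD at both follow-up visits. The following are assumptions, because the documents give no values:
- correlation between visits 0.7 (0.5 also tried);
- 10% to 20% missing at day 90;
- log-odds of missing day 90 rising by 1.0 to 1.5 per SD of a worse day 30 score.

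At 20% overall loss with the steeper slope, about 28% of the control arm and 12% of the experimental arm are missing.

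| Correlation 0.7, loss depends on day 30 score | Completer t-test estimate | Power |
|---|---|---|
| 10% loss, slope 1.0 | about 0.91 SD | about 77% |
| 20% loss, slope 1.5 | about 0.83 SD | about 65% |

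At correlation 0.5, 20% loss and slope 1.5, the completer estimate is about 0.87 SD with power of about 67%.

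**4. The repeated-measures model on the same data.** Its estimate is about 0.95 SD throughout. At 20% loss and slope 1.5, power without baseline is about 76–77% at correlation 0.7 and about 74% at 0.5. With baseline as a covariate, equally correlated with both follow-up visits, it is about 95% and 82%. Most of the power gain therefore comes from the baseline score.

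**5. Loss depending on the unseen day 90 score.** At 20% loss, correlation 0.7 and slope 1.5, completers give about 0.78 SD and the model without baseline about 0.86 SD, against a true 0.95. The bias is reduced but not removed.

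**6. No site effect, same dropout rule in both arms.** The completer difference is about zero, and the t-test rejects in about 5% of trials.

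**The case against.** The strongest reply is that the plan leaves its analysis open rather than choosing a bad one. A reader might infer that separate t-tests will be run at each visit, with day 30 data deliberately set aside. The text does not say so: it names no visit or analysis set and leaves room for further methods. That stands, and the defect is an unspecified analysis. It does not rescue the plan, because every method actually named for comparing continuous scores drops patients without a day 90 value, and the open-ended sentence commits to nothing before the data are seen.

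Second, nothing in the documents shows that poor responders will stay away. Follow-up is short, contacts are frequent, and patients are under chronic management for their condition. This also stands: the dropout pattern is an assumption. Random loss of 10% costs little, at 79.1% power. A reader might infer that the stated power is lost outright, but the documents give no dropout rate to support that. The loss becomes material from about 15% to 20%.

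Third, the effect size is tied to no scale or visit, so day 90 need not be the powered endpoint. That is true. Days 30 and 90 are listed on an equal footing, and the argument applies to whichever visit has missing scores.

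Fourth, a reader might infer that a repeated-measures model avoids the problem entirely. It does so for bias only if missingness depends on recorded scores. Without baseline adjustment it does not restore 80% power at 20% loss either.

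**Conclusion.** The point holds in a limited form. The plan has no analysis set, missing-data method or dropout allowance, and it names only tests that use patients with a score at the visit analysed. Under the assumed outcome-related loss of 10% to 20%, a true 0.95 SD difference is diluted to about 0.91 to 0.83 SD, and power falls to about 77% to 65% from 83.3% with complete data. These sizes rest on assumed dropout rates, slopes and a correlation of 0.7.

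The modelled harm is a diluted estimate and a possible false negative. A reader might infer a risk of false positives; the calculations show none when there is no site effect and both arms share one dropout rule. If the rule differed between arms, the direction of bias could change. The change is worth making before data are seen, but the documents do not show that the trial will fail without it.

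**What to change.** **In the Analytical Plan:**
- Analyse the questionnaire scores with a likelihood-based repeated-measures model. Include arm, visit, arm-by-visit, baseline score and baseline-by-visit, with unstructured covariance and small-sample degrees of freedom.
- Include all randomised patients with at least one post-injection score, by randomised arm. Patients with no post-injection score do not enter this model, so report their number by arm.
- Report the arm difference at each visit with its 95% confidence interval, and name the scale and visit on which the main conclusion rests.
- Add a sensitivity analysis in which day 90 scores are missing not at random.

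**In the Power Analysis:** state the expected dropout and give power at the expected number of day 90 scores, not only at 38 to 40.

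**Cost:** new wording and a standard model on scores already scheduled, with no new visits or patients. The main analysis would rely on a missing-at-random assumption, and the power quoted for the simple t-test would look slightly less favourable.

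### The open-ended regression search for independent predictors is not supported by 40 patients and should give way to one pre-specified, baseline-adjusted site model

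*Combined protocol and SAP*

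**What the plan says.** The Analytical Plan gives the regression one sentence: "Regression analysis will be performed to identify independent outcome predictors". Neither that section nor any other names the dependent variable, visit, candidate list, model type, selection rule, cap on terms or multiplicity control for it. The analysis is not described as exploratory. The sentence before it assigns the arm comparison to simple tests: "Comparison between groups will be done using chi square tests for proportions, and t-tests or ANOVA procedures for continuous variables". The sentence after it leaves the rest open: "Other inferential statistical analysis will be conducted as appropriate".

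Possible candidates appear under Subject selection criteria: "Other extracted information will include their past medical history, such as comorbidities, current medications, and any symptoms of IC they experience". That section also mentions review of examination, laboratory, intra-operative and pathology findings. The visit schedule under Design adds items recorded after injection: the Week 2 post-void residual, and medications and adverse events at every later contact.

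On size, Power Analysis says "we calculated a minimum total study group requirement of 38 subjects with 19 subjects in each arm", and Sample Size and Randomization says "Each study arm will consist of 20 subjects for a total study population of 40". Outcome Measure(s) makes the PUF "questionnaire and the O'Leary-Sant Symptom and Problem Indexes" primary, at 30 and 90 days, without ranking the scores or the visits.

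**The concern.** To call a variable an independent predictor is to claim that its coefficient stands after adjustment for the others. That needs a short list fixed in advance and a sample sized for it. Here the list is open and the sample was sized for something else. Three things are at stake.

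- Chance associations may be reported as independent predictors, while real ones of moderate size are often missed.
- Nothing keeps out variables recorded after injection. Injection site may affect these, and adjusting for them can remove or distort the randomised comparison.
- If site is one of the regression terms, the site effect is available from both a t-test and a regression, and the plan does not say which one counts.

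**Working it through.** 1. **The plan's own figure.** Inputs from Power Analysis: d = 0.95 and alpha 0.05. The 0.80 printed there as beta is read as power, because that reproduces the stated number. Sidedness is not stated; two-sided is assumed. A two-sample t-test (noncentral t) needs n = 18.4 per arm, rounded up to 19, total 38, which matches. Power is 0.813 with 19 per arm and 0.833 with the planned 20. A one-sided test needs 15 per arm and does not match. The calculation therefore covers the difference between arms and no regression coefficient.

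2. **False predictors.** With k independent null candidates tested at 0.05, P(at least one false) = 1 − 0.95^k. The documents do not give k, so a range is shown.

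| k (assumed) | 3 | 5 | 8 | 10 | 15 |
|---|---|---|---|---|---|
| P | 14% | 23% | 34% | 40% | 54% |

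Backward elimination was also simulated: 40 patients, 20 per arm, no site effect, site plus 5 or 8 independent normal covariates, none or one of them truly correlated 0.5 with the outcome, 4,000 runs each. At least one null term was kept in 23.2% to 28.0% of trials with five covariates and 35.5% to 39.4% with eight. The R² expected from noise alone is p/(n − 1): 6/39 = 0.15 with six terms and 9/39 = 0.23 with nine.

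3. **Real predictors.** Fisher z for r = 0.3, n = 40: atanh(0.3) × √37 = 0.3095 × 6.083 = 1.883. Power = Φ(1.883 − 1.960) = 0.47. A noncentral-F calculation for one coefficient gives 0.49 at a partial r of 0.3 and 0.24 at 0.2. It reaches 80% at a partial r of 0.41 to 0.42. With Bonferroni over six to nine terms, power at 0.3 falls to 0.23 to 0.18.

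4. **Site effect, if site is a term.** Same simulation, true site effect zero, one outcome:
   - t-test alone: 0.049 to 0.058.
   - One full regression alone: 0.049 to 0.057.
   - Smaller p-value of those two: 0.069 to 0.087.
   - Smallest p-value over all 2^5 = 32 subsets of five covariates (2,000 runs): 0.087 and 0.116.

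   Simulation error is about 0.4 percentage points (0.7 for the subset search). The t-test's 0.058 shows that one setting ran slightly high by chance.

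5. **Scores and visits.** Three scores at two visits give six results. With an assumed correlation of 0.6 among them, t-tests alone give at least one false positive with probability 0.19. Allowing the t-test or the regression for each gives 0.24.

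6. **Baseline adjustment.** Adjusting for the day-0 score turns d into d/√(1 − ρ²), where ρ is the baseline-outcome correlation (not given in the documents). For d = 0.95 and 20 per arm, ignoring the one degree of freedom spent:

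| ρ (assumed) | 0 | 0.3 | 0.5 | 0.7 |
|---|---|---|---|---|
| Power | 0.83 | 0.87 | 0.92 | 0.98 |

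**The case against.** The best defence is that the plan assigns the arm comparison to t-tests, ANOVA and chi-square, and gives regression a separate sentence and a separate purpose. On that reading the regression is a side analysis that leaves the site result alone. This stands in part. The documents never say that site enters the regression. It is the natural reading, because site is the only predictor they hypothesise about, but the type I error figures for site depend on it.

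A reader might infer four stronger things that the documents do not support.

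- *That 40 patients can identify no predictor at all.* A single strong one can be found. The planning effect itself corresponds to r = 0.95/√(0.95² + 4) = 0.43, just above the 80% threshold.
- *That every abstracted item is a candidate.* Subject selection criteria commits to taking only as much clinical data as is needed, and examination, laboratory and pathology findings are listed for review, not for modelling. The candidate counts here are assumptions.
- *That the regression doubles the error rate.* About 10% requires searching every covariate subset and keeping the best result, and no such search is described. One pre-specified regression used alone stays near 5%. Most of the inflation across the trial comes from the unranked scores and visits.
- *That post-injection variables will be adjusted for.* No section proposes this. The point is only that none rules it out, and no size can be put on it.

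The gap itself remains: a stated aim of finding independent predictors, with no candidate list, no selection rule and no exploratory label.

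**Conclusion.** The concern holds in a limited form, as a cheap improvement. A sample sized for one two-group difference does not support a reliable list of independent predictors. Over the assumed range of candidates, a false predictor is anything from an occasional to a more-likely-than-not result, and a real predictor of moderate size is found about half the time. These figures rest on independent null candidates and on all 40 patients being evaluable, which is the favourable case.

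The effect on the site comparison is conditional and modest: a few percentage points for one outcome if site is a term and the result may be chosen between analyses. Across six results it adds about 5 points (0.19 to 0.24) to inflation that is already there without any regression. Ranking the scores and visits therefore matters more, but would not by itself settle which analysis supplies the site effect.

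**What to change.** Replace the regression sentence with the following.

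- One pre-specified model containing arm and the day-0 value of the same score, for one score and one visit that the sponsor names as primary. The site effect is taken from that model only.
- The same model for the remaining scores and visits, labelled secondary.
- No variable recorded after injection as a covariate; this names the Week 2 residual, new medications and adverse events.
- Any other predictor association reported as exploratory, with confidence intervals and without the claim of independence.

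The cost is a change of wording. Day-0 questionnaires are already in the visit schedule, so no new data are needed, and the adjustment should add power as in step 6. The entry thresholds on the questionnaire scores may narrow the day-0 range, so the smaller gains in that table are the prudent ones to expect. The downside is that the trial gives up a predictor claim, one that its size does not support. The sponsor must also choose one primary score and visit, because the fix depends on that choice.
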